The Impact of Exercise on Subthalamic Nucleus Neural Activity in Parkinson's Disease

Study Protocol

NCT05905302

Document Date 2/14/2023

Posted 9/16/2025

Project Title: The impact of exercise on subthalamic nucleus neural activity in Parkinson's disease

PI: [name]

Version Date: 2/14/2023

APPROACH

Fifteen PwPD utilizing the Percept PC DBS system will be enrolled for this project. Briefly, all patients will be at least six-months post bilateral DBS surgery with DBS parameters clinically optimized for at least three months prior to enrollment. To reduce possibility of a cardiac adverse event during the proposed exercise sessions, the American College of Sports Medicine (ACSM) Pre-exercise Screen¹ will be performed prior to exercise (see Protection of Human Subjects for details). We anticipate an ample population of PwPD eligible for recruitment as neurosurgeons within the Center for Neurological Restoration (CNR) perform 200 bilateral STN DBS surgeries annually. The Percept platform is rapidly becoming the system of choice due to ease of programming.

Following all pre-screening, participants will complete three visits on 3 separate days. For **Visit 1**, participants will complete the informed consent process, establish resting heart rate (HR; supine x 5 min), be fitted to the cycle to ensure proper mechanics, complete ~5-10 minutes of FE and VE to ensure safety and understand cycle operation, complete 5-10 familiarization force-tracking trials,² and have order of FE or VE assigned for Visit 2 and 3 via a computerized randomization scheme. Target HR will be calculated using the Karvonen method³ [(Max HR-Resting HR) x (60%-80%) + Resting HR]; max HR will be estimated as (220-age).⁴ Figure 1 provides an overview of the experimental paradigm for Visit 2 and 3.

For **Visit 2 and 3**, PwPD will arrive OFF antiparkinsonian medication and On-DBS. The 130-minute experimental session will be divided into four epochs: 1) On-DBS, 2) Off-DBS, 3) Off-DBS + Exercise and 4) Post-exercise. Neural activity from the STN will be continuously recorded from both DBS electrodes for the entire 130-minute session.

To ensure proper autonomic and hemodynamic response to exercise, BP will be taken before, during (minute 20), and following cool-down. During exercise sessions, pedaling torque, cadence and HR will be continuously recorded at 60Hz and rate of perceived exertion (RPE) will be recorded every 10 minutes using our previous methods.⁵ The main exercise set (40 min) and HR (60-80% of HHR)⁶ will be identical across FE and VE. The single manipulated independent variable is pedaling cadence. For the VE group, maximum cadence will be limited to 60rpms. During FE, with assistance of the motor, cadence will be maintained between 80-90rpms.⁶ This approach replicates previous human and animal exercise paradigms and will lead to clear interpretation of the effect of cadence on STN neural activity and upper extremity motor function.

Forced-exercise (FE) Cycle and Session: To deliver the FE intervention, a suite of sensors is integrated into a standard stationary cycle to monitor system and rider status. The inertia wheel, brake and brake controller

[figure not shown]

Figure 1: Illustration of experimental protocol and equipment utilized to obtain LFPs from STN-DBS implanted in PD patients during exercise. (A) Percept PC system is integrated into the implantable pulse generator (IPG) shown in circle insert and continuously transmits LFPs in real time wirelessly to a storage device (tablet) (B) Illustration of the DBS lead implanted in the subthalamic nucleus (STN) and surrounding basal ganglia nuclei (C) Assessments, MDS-UPDRS-III and force-tracking, will be performed at 3 time points during an experimental session.

were replaced with three core components: servomotor, motor-drive, and programmable controller. While the motor augments pedaling rate in the FE mode, participants actively contribute to pedaling as they must exercise within their specified target HR range. The control algorithm automatically adjusts assistance or resistance during FE based on the user's continuously-monitored torque production and heart rate thus allowing the system to maintain an effective therapeutic cadence while the user maintains their target heart rate.

Voluntary Exercise (VE) Session: During the VE session, individuals will complete the main exercise set at a cadence of no greater than 60rpms⁶ on the same stationary cycle while in its standard voluntary mode. In the event that a participant's voluntary rate is >60rpms, resistance will be applied to ensure cadence is maintained and target HR is reached. In standard voluntary mode the motor control assistance algorithm is disabled and the cycle functions as a typical resistance based stationary cycle. During the VE exercise session, pedaling torque, cadence and HR will be continuously recorded at 60Hz and RPE will be recorded as in the FE session.

DATA COLLECTION

Local Field Potentials (LFP) Recordings: Neural activity of the STN will be gathered bilaterally for the duration of each 130-minute visit. Medtronic's BrainSense Indefinite Streaming platform will provide LFP data from Medtronic 3389 electrode model or SenSight directional leads. For the **On-DBS epoch**, LFPs from contact pairs surrounding the stimulating contact (0-2, 0-3, 1-3) for each hemisphere will be recorded (2 channels total).⁷ In the **Off DBS, Exercise and Post-exercise epochs**, LFPs will be recorded between contact pairs 0-2, 0-3, 1-3 bilaterally resulting in simultaneous recordings of 3 channels per hemisphere (6 channels total). All LFP recording will be sampled at 250Hz and low-pass filtered (0-100Hz) and streamed via Bluetooth to the Medtronic tablet (Figure 1A&B). While in the Off DBS epoch, the bipolar channel with highest peak power in the beta band (13–35 Hz) during rest in each hemisphere will be selected for further analyses. This selection is based on previous studies demonstrating a significant correlation between contact-pair location in the sensorimotor portion of the STN and beta power.⁸ **LFP outcomes:** Prior to calculation of outcomes, windows containing movement artifacts will be visually identified by large fluctuations in the time series and high amplitude broadband activity in the spectrogram and removed from further analysis. Triggered spectrograms will be calculated for each trial using the multitaper method with a 500 ms, 250 ms overlap moving window, 2.0 Hz frequency resolution, and 1 taper. Relative power will be obtained for each subject and frequency by normalizing the absolute power by its average across time for each channel. This approach will facilitate comparison across subjects, whose absolute signal magnitude can vary by one or two orders of magnitude. The relationship of synchronization and desynchronization changes in oscillatory activity within the frequency bands of interest, delta, theta, alpha, beta and gamma bands, will be calculated across each of the four epochs within an experimental session. Along with average power, moment-to-moment dynamics of the band power, e.g., beta bursts, will be assessed in each condition as previous data indicate beta burst activity during continuous movement is related to PD bradykinesia.⁹ [name] will lead the collection and analysis of LFP data.

Force-tracking: Upper extremity motor control will be assessed during the performance of a force-tracking task used previously with older adults^{10,11} and PwPD.^{2,12} Patients will use a precision grip (thumb and index finger) with the dominant hand to exert an isometric force against a six-degree of freedom force transducer (Figure 1C) affixed to an adjustable experimental table. The greatest force produced in the F_Z axis (grip force) during a five second trial will be considered their maximum voluntary contraction (MVC). To ensure consistent motor task demands across the four data collection timepoints, target tracking force will be 20% of their MVC for a given session. During the force-tracking task, participants match their grip force to the target force as accurately as possible; a monitor simultaneously displays target force and patient produced grip force.

Force-tracking Outcomes: Force data will be filtered with a phase-symmetric low-pass filter employing Woltring's algorithm using existing Matlab analysis programs.^{13,14} The primary outcomes will be time within the target range (TWR) and relative root mean square error (RRMSE). The TWR is calculated by determining the time the patient's force trace is within $\pm 2.5\%$ of the target line. The TWR provides an overall accuracy measure of force-tracking. To account for differences in the amplitude of the target force (e.g. inter-patient and intra-patient variability due to stimulation or exercise status), the RRMSE will be used as a method of normalizing

performance relative to force amplitude. Where, $F_T(t)$ is the target force provided to the patient, $F_0(t)$ is the force produced by the patient, T trial time.

Aim 1: To determine the effects of two modes of high intensity exercise, FE and VE, on the pattern of neural activity within the STN.

Statistical Analysis: Average band powers (delta, theta, alpha, beta and gamma) will be calculated at rest for 90 seconds in the Off DBS session immediately prior to exercise and immediately following FE and VE sessions. Mixed effect models will be utilized for each band power to determine if band powers at rest while Off DBS are significantly reduced following high intensity exercise (primary outcome), and to determine if the FE reduces band power significantly more than VE (secondary outcome).

Aim 2: To determine the relationship between changes in STN neural activity associated with FE and VE on upper extremity motor function and clinical symptoms of PD.

Statistical Analysis: The force-tracking outcomes, including TWR, will be calculated for all trials. Data from the Off DBS and Off DBS + Post Exercise sessions will be used for the primary analysis. Mixed effects models will be utilized to determine if force tracking performance improves following either exercise mode compared to Off-DBS and secondary analysis will be conducted to determine if FE improves force tracking more than VE. Clinical data from the same time points will be evaluated to determine the overall clinical response to high intensity exercise and any differential effects of exercise mode (FE vs. VE). Mixed models will be adjusted for confounding characteristics determined a priori, including sex, education, and PD severity. Model assumptions and model fit will be assessed, and variables will be transformed, as needed.

Inclusion Criteria:

- a) Adult with a diagnosis of PD by a movement disorders neurologist
- b) Previous placement, at least six months, of bilateral Medtronic Precept DBS as standard of care treatment for their PD.
- c) Stable and clinically optimized DBS parameters for three months prior to enrollment.
- d) Demonstrate the ability to safely mount and dismount a recumbent exercise cycle with an upright back.
- e) Willingness to withhold antiparkinsonian medication and DBS stimulation.
- f) Exercise clearance using the American College of Sports Medicine (ACSM) Pre-participation Health Screen
 - a. If the ACSM screen recommends medical clearance, the subject must obtain medical clearance by their health care provider prior to participation.
 - b. Those who choose not to obtain physician clearance will not be eligible for participation.

Exclusion Criteria:

- a) Diagnosis of dementia or any neurocognitive impairment that compromises the ability to provide informed consent.
- b) A musculoskeletal issue that limits one's ability to cycle
- c) Neurological disease other than Parkinson's disease (i.e. multiple sclerosis, stroke) that impacts motor or cognitive function
- d) Uncontrolled cardiovascular risk factor such as a current cardiac arrhythmia, uncontrolled hypertension, untreated deep vein thrombosis, etc.

REFERENCES

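### The plan credits any FE-VE difference to cadence alone, but motor assistance changes with cadence in every session, so the two cannot be separated

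*Combined protocol and SAP*

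**What the plan says.** The Approach section, in the text on Visits 2 and 3, makes three linked statements about the contrast between FE and VE.

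- On what is held constant: "The main exercise set (40 min) and HR (60-80% of HHR)⁶ will be identical across FE and VE".
- On what is varied: "The single manipulated independent variable is pedaling cadence".
- On what follows: the approach "will lead to clear interpretation of the effect of cadence on STN neural activity and upper extremity motor function".

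The two session descriptions then say how each mode is delivered. FE is held at 80-90 rpm with the motor's help. Under Forced-exercise (FE) Cycle and Session: "While the motor augments pedaling rate in the FE mode, participants actively contribute to pedaling". A controller there raises or lowers assistance or resistance in response to the rider's torque and heart rate. VE is capped at 60 rpm. Under Voluntary Exercise (VE) Session: "In standard voluntary mode the motor control assistance algorithm is disabled". If a participant's own rate goes above 60 rpm, "resistance will be applied to ensure cadence is maintained and target HR is reached".

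The statistical paragraphs of Aims 1 and 2 compare FE with VE as modes of exercise and do not mention cadence. In both aims that comparison is secondary to the question of change after exercise. Torque, cadence and heart rate are recorded at 60 Hz and perceived exertion every 10 minutes, but neither aim's analysis says how these will be used.

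**The concern.** A claim that only one variable is manipulated tells the reader that any difference between arms can be credited to that variable. Here the two modes differ in at least two delivered features, pedalling rate and motor assistance, and these always change together.

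What is at stake is the mechanistic conclusion. If band power or force tracking changed more after FE than after VE, the Approach section would license the statement that faster pedalling caused it. The same data would fit an effect of being assisted by a motor, or any mixture of the two. The comparison of modes is not at stake, and nor is the primary before-versus-after question.

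**Working it through.** The plan gives no figure to reproduce, because the claim concerns what the design can identify. The check sets out the design and counts what can be estimated.

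**Inputs**
- FE: 80-90 rpm, assistance algorithm active (Approach, Visits 2 and 3; Forced-exercise section).
- VE: at most 60 rpm, assistance algorithm disabled (Approach; Voluntary Exercise section).
- 15 patients, each with one FE and one VE session in randomised order (Approach).

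**Step 1: the cells of the design**

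| | Assistance active | Assistance disabled |
|---|---|---|
| 80-90 rpm | FE | none |
| 60 rpm or less | none | VE |

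Two of the four cells are empty.

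**Step 2: what can be estimated.** Code high cadence as C = 1 or 0 and assistance as A = 1 or 0. Every FE session has (C, A) = (1, 1) and every VE session has (0, 0). Write the mean outcome as b0 + bC x C + bA x A. Then

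mean(FE) - mean(VE) = bC + bA.

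Only the sum is identified. If the observed difference is D, then bC = D with bA = 0 fits exactly as well as bC = 0 with bA = D, and so does any other pair adding to D.

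**Step 3: numerical confirmation.** With 15 x 2 = 30 sessions, the design matrix with columns for intercept, C and A has rank 2. Adding patients adds copies of the same two rows, so the rank stays at 2. Patient-level covariates such as sex, education and severity do not help, because the C and A columns remain identical.

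**Step 4: could variation within FE help?** The amount of assistance will vary between and within FE sessions. That variation is not assigned: the controller sets it from the rider's own torque and heart rate. It therefore gives no randomised information about assistance separate from cadence.

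**Step 5: how tightly intensity is matched.** The target is a range: "Max HR-Resting HR) x (60%-80%) + Resting HR", where "max HR will be estimated as (220-age". I read HHR as heart rate reserve, in line with this formula. The width of the band is 0.20 x (220 - age - resting HR). The documents give no ages or resting rates, so these are assumptions:
- Age 65, resting HR 70: reserve = 220 - 65 - 70 = 85. Lower limit = 0.6 x 85 + 70 = 121 bpm, upper limit = 0.8 x 85 + 70 = 138 bpm, width 17 bpm.
- Over ages 50-80 and resting HR 60-80, the width runs from 0.20 x 60 = 12 bpm to 0.20 x 110 = 22 bpm.

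This is how far apart two compliant sessions of one patient could be at the extreme. It does not predict that they will differ. It is a reason to report what was achieved.

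**The case against.** The best defence is that the motor is simply the means by which cadence is raised, so assistance belongs to the cadence manipulation, and that both aims already compare modes. The second half stands and limits the point: no planned test or estimate is labelled a cadence effect. The first half does not rescue the sentences. A device that shares the pedalling work does more than set a rate, and no session shows what the rate does without it. Following earlier exercise paradigms does not fill the empty cells.

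A reader might infer four stronger criticisms. The documents do not support them.

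- *That heart rate is wrongly called identical.* The sentence puts the 60-80% range in parentheses and fairly reads as the same target band for both modes. Both modes are steered towards it: the FE controller responds to heart rate, and VE resistance serves the heart-rate target. Nothing shows a systematic difference in intensity.
- *That VE requires 33-50% more torque.* The ratios 80/60 = 1.33 and 90/60 = 1.50 hold only at equal external power. The plan matches heart rate, not power, and the motor contributes in FE, so the actual torque ratio is unknown. Torque may well differ, but largely as a consequence of the mode rather than as a separate manipulation.
- *That resistance is a feature of VE alone.* It is described for VE when the voluntary rate exceeds 60 rpm, and the FE controller can apply resistance too.
- *That adjusting for achieved heart-rate reserve would repair the comparison.* Achieved intensity arises after randomisation, there are only 15 patients, and the adjustment leaves cadence and assistance just as aliased. It could give false reassurance.

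**Conclusion.** The single-variable statement and the promise of a clear cadence interpretation are wrong as written. Cadence and motor assistance are completely aliased: two factors, one identifiable contrast, at any sample size and with any covariates. This rests only on the plan's own descriptions, with FE delivered with the assistance algorithm active, VE with it disabled, and no other type of exercise session in the experiment. It does not depend on the assumed ages or resting heart rates.

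The scope is narrow. FE versus VE remains a valid randomised-order, within-patient comparison of two exercise modes. The primary question of change from before to after exercise is unaffected. No test, estimate or sample size changes. What fails is the attribution of a secondary difference to cadence. Severity is minor.

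**What to change.** **Wording.** Replace the two sentences in the Approach section with a statement in line with Aims 1 and 2, for example:

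> FE and VE are two exercise modes that differ in pedalling cadence and in motor assistance and, as a consequence, possibly in torque and work. Differences between them will be interpreted as differences between modes and will not be attributed to cadence alone.

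**Reporting.** Pre-specify one descriptive table for the 40-minute main set. For each mode, show achieved mean percentage of heart-rate reserve, cadence, torque and perceived exertion, with the within-patient FE-VE difference and its confidence interval. Percentage of reserve is 100 x (mean HR - resting HR) / (220 - age - resting HR), using the resting value from Visit 1. The table shows how closely intensity was matched within the common band. It does not separate cadence from assistance and should not be presented as doing so.

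**Cost.** Two sentences and one table from data already recorded. The exercise prescription does not change. The downside is a more modest mechanistic claim.

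### The resting-beta test for a fall after exercise uses a channel chosen for high resting beta, and the text does not keep the selection data apart from the baseline

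*Combined protocol and SAP*

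**What the plan says.** - **Selection.** Data Collection, Local Field Potentials (LFP) Recordings: outside the On-DBS epoch, pairs 0-2, 0-3 and 1-3 are recorded on both sides, "resulting in simultaneous recordings of 3 channels per hemisphere (6 channels total"). One pair per hemisphere is kept: "While in the Off DBS epoch, the bipolar channel with highest peak power in the beta band" (13–35 Hz) during rest. The stated reason is a "significant correlation between contact-pair location in the sensorimotor portion of the STN and beta power".
- **Baseline and test.** Aim 1, Statistical Analysis: average band powers "will be calculated at rest for 90 seconds in the Off DBS session immediately prior to exercise and immediately following FE and VE sessions". Mixed models are used "to determine if band powers at rest while Off DBS are significantly reduced following high intensity exercise (primary outcome"). FE versus VE is secondary.
- **Normalisation.** LFP outcomes: "Relative power will be obtained for each subject and frequency by normalizing the absolute power by its average across time for each channel".
- **Design.** Approach: 15 participants attend both exercise visits, with FE and VE in random order. No session without exercise is described. For the session layout the text says "Figure 1 provides an overview of the experimental paradigm for Visit 2 and 3"; that figure is not available here.

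The text does not give the length or position of the rest segment used for selection. It does not say whether that segment excludes the 90-second baseline, or whether the pair is chosen once or at each visit.

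**The concern.** A pair can rank highest because its beta is truly high, or because its beta happened to be high while the ranking was made. The second part does not persist. If the same fluctuation is present in the baseline, the chosen pair starts too high and falls back afterwards, whether or not exercise does anything. The primary beta test looks for exactly that fall.

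Nothing else stated in the plan would reveal this. Both randomised visits contain exercise, and no selection-free analysis is planned. A small reported fall in resting beta could therefore be partly a product of the choice of channel, and a reader could not tell how much.

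**Working it through.** The plan gives no alpha, SD or power figure, so there is nothing to reproduce.

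**Inputs from the documents.** 15 patients, 2 hemispheres, 2 exercise visits, 3 candidate pairs, a 90-second segment, 500 ms windows with one taper and 2 Hz resolution.

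**Assumed inputs (not in the documents).** Analysis on ln power; two-sided alpha 0.05; SD between pairs *sb* = 0.4; window-to-window SD *sw* = 0.15; SD of the patient-level change 0.10; noise correlation between pairs *ρ*; correlation *r* between selection noise and baseline noise (*r* = 1 is full overlap); pair chosen anew at each visit; no true exercise effect.

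**Step 1: formula.** The expected maximum of three standard normals is 3/(2√π) = 0.846. With equal *ρ*, the expected spurious ln change is

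−0.846 · r · sw²(1−ρ) / √(sb² + sw²(1−ρ)).

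For *ρ* = 0.5 and *r* = 1: sw²(1−ρ) = 0.0225 × 0.5 = 0.01125, and √(0.16 + 0.01125) = 0.414. The result is −0.846 × 0.01125 / 0.414 = −0.023, a fall of about 2.3%. At *r* = 0.5 it is half that.

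**Step 2: simulation.** Patient-mean change, one-sample t-test:

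| Noise correlation between pairs | Fall, error at r = 1 | Fall, error at r = 0.5 |
|---|---|---|
| 0.5/0.5/0 | 3.0%, 11% | 1.5%, 7% |
| 0.5 | 2.3%, 8–9% | 1.1%, 6% |
| 0.82/0.82/0.5 | 1.3%, 6% | 0.6%, about 5% |
| 0.8 | 1.0%, 5.5% | 0.5%, 5% |
| 0.9 | 0.4%, 5% | 0.2%, 5% |

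At *r* = 0 the bias is about zero and the error nominal. The excess lies in the direction of a fall: at *r* = 1 the false-fall rate (nominal 2.5%) is 11.0%, 7.6% and 5.4% in the first three rows.

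**Step 3: sensitivity to the assumptions.**
- Estimation noise only: 1/√(90 × 22) = 2.2% for the 13–35 Hz average. The bias is about 0.001 or less and the error nominal.
- Pairs with similar beta power (*sb* = 0.2, *ρ* = 0.5, *r* = 1): −0.846 × 0.01125 / √(0.04 + 0.01125) = −0.042, with 18% error.
- Patient-change SD 0.20 instead of 0.10: error at *r* = 1 is at most about 8%.
- Over a grid of 140 assumed settings, error was at most 6% in 96 and above 10% in 15. Of those 15, 14 had *sb* = 0.2. These counts describe the grid and are not probabilities.

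**Step 4: the rule as written.** Selection uses peak beta and the test uses average beta. The settings are "multitaper method with a 500 ms, 250 ms overlap moving window, 2.0 Hz frequency resolution, and 1 taper". I modelled 11 bins of 2 Hz, 180 independent windows (bin noise 1/√180 = 7.5%), a beta peak three times background, full overlap and *sb* = 0.4. The fall is 0.3% with 5% error for estimation noise alone, 0.5–1.2% with 5–7% if the peak also varies 15% between windows, and 1.4–3.5% with 7–17% if it varies 30%.

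**Step 5: does normalisation help?** If the divisor *m* is the channel's average over the whole session, then ln(post/m) − ln(pre/m) = ln(post) − ln(pre), and the bias is unchanged. The plan does not say over what time the average is taken, so this is conditional.

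**Step 6: FE versus VE.** With selection at each visit, bias stayed within 0.003 and error between 4.3% and 6.0%. If the pair is fixed from the first exercise visit's own baseline, the overall bias is −0.015, all of it from that visit (−0.030). Random order balances this on average, and an 8/7 split leaves 0.030/15 = 0.002.

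**The case against.** **The segments may differ.** A reader might infer that selection and baseline use the same 90 seconds. The documents do not say so. Selection is described as rest within the Off-DBS epoch, the baseline as a particular 90 seconds just before exercise, and Figure 1 might show separate segments. This stands: full overlap is an upper case. But the text does not exclude overlap, and a separate segment close in time could share slow fluctuation with the baseline.

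**The effect may be negligible.** This also stands. Fluctuation common to all three pairs does not affect which is chosen and adds no bias. Most assumed settings give near-nominal error. It would be wrong to infer that a beta fall in this trial must be an artefact.

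**The scope is narrow.** A reader might infer that all five bands and the FE–VE comparison are biased. Only beta is selected on. Other bands are affected only through noise correlated with beta, and FE versus VE is unbiased if selection works alike at both visits. The lack of a session without exercise is a wider limitation of any pre–post claim and adds no weight of its own here.

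**The rule is prespecified and has an anatomical rationale.** That is a reason to keep the selection, but it does not prevent regression to the mean.

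**An all-pairs model cannot measure the bias.** Correct. A smaller all-pairs fall can come from selection bias or from dilution by pairs outside the sensorimotor STN, so that analysis can only be supportive.

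**Conclusion.** The point holds in limited form. The stated rule can bias the primary pre–post test of resting beta toward the hypothesised fall, to the extent that selection and baseline data overlap or share pair-specific fluctuation. The text neither separates them nor provides an analysis free of the selection. Under the middle assumptions at full overlap, the size is a 0.4–3% fall with 5–11% two-sided error. It could be close to zero, or larger if pairs have similar beta power, and the documents do not allow a choice between these. Severity is minor to moderate. Confidence in the mechanism and direction is good; confidence in any particular size is low.

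**What to change.** 1. **Choose each visit's pair on Off-DBS rest data from the other exercise visit.** The selection data are then never that visit's own baseline. In simulation this removed the bias (within 0.001, error 4.8–5.4%), assuming noise independent between days. The cost is that the chosen pair may differ between visits. If one pair must serve both visits, choose it on an Off-DBS rest segment that excludes the 90-second baselines, and state the segment and visit. Such a pair keeps some bias if beta drifts slowly: 0.2–1.1% in the cases run, with assumed gaps of 5 or 10 minutes. A segment very early in the epoch also follows closely on the end of stimulation and may not represent settled Off-DBS rest.

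2. **Add a sensitivity analysis of resting beta with all three recorded pairs per hemisphere**, reported beside the selected-pair result. Include a visit term and a patient-level random pre–post change, because the 3 × 2 × 2 = 12 changes per patient are not independent. In the middle case, error was 4.2% with that random effect, 16% with hemisphere-visit effects only, and 30% with all 15 × 12 = 180 changes treated as independent. The cost is dilution: for a ln change of −0.10 in the top pair only, the all-pairs estimate is −0.034 with 16% power, against 56% for the selected pair. If all pairs change equally, it has 81% against 69%. It should therefore not replace the selected-pair result, and a smaller all-pairs fall should not by itself be read as selection bias.

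Both changes need only SAP wording and one extra model. All three pairs are already recorded before, during and after exercise.

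### LFP windows are rejected by eye before band power is calculated, with no masking to exercise mode or pre/post and no numerical rule stated, so uneven rejection could bias the primary contrast in either direction

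*Combined protocol and SAP*

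**What the plan says.** The paragraph on LFP recordings under DATA COLLECTION sets the rejection rule: "windows containing movement artifacts will be visually identified by large fluctuations in the time series and high amplitude broadband activity in the spectrogram". These windows are then "removed from further analysis", and this happens before any outcome is calculated. The spectral settings are "500 ms, 250 ms overlap moving window, 2.0 Hz frequency resolution, and 1 taper". The paragraph ends by naming one individual who "will lead the collection and analysis of LFP data".

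Under Aim 1, Statistical Analysis, average power in five bands is "calculated at rest for 90 seconds in the Off DBS session immediately prior to exercise and immediately following FE and VE sessions". The primary question is whether band power falls after exercise. The secondary question is whether it falls more after FE than after VE.

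The documents state no amplitude or power threshold, second reader, minimum clean duration, report of the share rejected, or analysis without rejection. They mention no masking of any kind.

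**The concern.** Mean power is the outcome, and one of the two signs used to delete a window is that its power looks high. A subjective exclusion that overlaps with the outcome is safe only if it is applied evenly to the segments being compared. The usual protections are a fixed rule or a reader who cannot see the condition, and the plan states neither.

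The bias can run both ways. Rejecting clean windows more readily after exercise, or leaving more artifact in before it, produces an apparent fall. The reverse hides a real one. The same applies to FE versus VE. The planned mixed models cannot correct this, because the deleted windows never reach them.

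**Working it through.** The plan gives no rejection rate, artifact size or standard deviation (SD), so there is no figure to reproduce. The steps below show how large the effect could be under stated assumptions.

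**Inputs from the documents.** Rest segments of 90 s (Aim 1); 500 ms windows overlapping by 250 ms, 2 Hz resolution, beta 13–35 Hz, signal to 100 Hz (LFP paragraph); 15 participants (APPROACH).

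**1. Windows per segment.** (90 − 0.5)/0.25 + 1 = 359. So 5% is about 18 windows and 10% about 36.

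**2. Artifact left in one segment only.** If a share c of windows stays in at m times normal power, the segment mean becomes 1 + c(m − 1). With c = 0.05 and m = 3 (both assumed), this is 1 + 0.05 × 2 = 1.10. Left in the post segment, it reads as a 10% rise. Left in the pre segment, the ratio is 1/1.10 = 0.909, a 9% fall. With c = 0.02 the mean is 1.04, and with c = 0.10 it is 1.20.

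**3. Clean windows rejected in one segment only.** Assume pure noise, with independent, exponentially distributed power in each 2 Hz bin. Summed power over k bins is then gamma with shape k. After dropping the top share d, ranked on that sum, retained mean/true mean = G(q; k + 1)/(1 − d). Here G is the gamma distribution function and q is the 1 − d quantile of the gamma with shape k. Beta covers (35 − 13)/2 = 11 bins; 2–100 Hz covers 50 bins. With a flat spectrum every bin falls by the same proportion as the total. The sloped spectra were simulated, with windows ranked on total power.

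| Windows ranked on | Fall in mean beta, top 5% dropped | Top 10% dropped |
|---|---|---|
| Broadband power, flat spectrum | about 1.6% | 2.9% |
| Broadband power, 1/f spectrum | 0.6% | 1.1% |
| Broadband power, 1/f² spectrum | about 0.1% | about 0.1% |
| Beta power itself | 3.8% | 6.6% |

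The written sign is broadband activity, so the first three rows are closer to the plan's rule. The last row applies only if the reader in effect picks windows on beta power.

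**4. Even rejection.** If the same share is rejected in the same way before and after exercise, the factor cancels in the post/pre ratio. If rejection is unrelated to mode, time and power, the expected bias is 0.

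**5. Consequence for the test.** Take one paired change per participant, n = 15, two-sided alpha 0.05 (assumed), and no true change. A bias b shared by all participants, with SD of change s, gives a noncentral t with 14 degrees of freedom and noncentrality √15 × b/s. The chance of a significant result (nominal 0.05) is:

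| Bias b | s = 10% | s = 20% | s = 30% |
|---|---|---|---|
| 3% | 0.19 | 0.08 | 0.07 |
| 5% | 0.44 | 0.15 | 0.09 |
| 10% | 0.95 | 0.44 | 0.23 |

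**The case against.** The strongest reply is that the rule targets movement artifact, not high beta. It uses two signs, and a narrowband beta burst is not broadband activity. This stands, and it is why the broadband rows above are the relevant ones. Overlap with the outcome remains, because broadband power contains the tested bands.

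A second reply is that both primary segments are recorded at rest. Pedalling artifact, where cadence differs by mode, falls outside them. Both modes also share a 40-minute main set and the same heart-rate target. This stands too: a reader might infer that artifact load differs before and after exercise or between modes, but the documents give no rates. Equality cannot be presumed either, since participants are off medication and off stimulation and the second segment follows exercise at once.

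Third, a reader might infer that the person rejecting windows is unmasked and knows each file's condition. The documents do not say so. They state who leads the work, not who marks windows or how files are labelled. The supportable statement is that no masking is stated and the reader could know.

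Fourth, the scenarios above are one-sided by construction. Random reader error adds noise, not bias.

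Fifth, a fixed threshold is not clearly better than expert review. It may keep artifact, and step 2 shows that retained artifact can move the mean more than over-rejection of clean noise does.

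**Conclusion.** The point holds as a gap in protection against bias, not as a demonstrated bias. The plan states a subjective exclusion that overlaps with its primary outcome and states no masking and no threshold, so the pre/post and FE-versus-VE contrasts are open to bias in either direction.

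The size cannot be known from the documents. One-sided over-rejection of clean noise on broadband power moves mean beta by about 3% at most in the cases examined. Residual artifact at three times normal power in 5% of one segment's windows moves that segment's mean by about 10%. Either matters for inference only if it is consistent across participants and not small relative to the SD of change, which the plan does not give.

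It might also be inferred that such a bias could never be found afterwards. The documents do not support that. The recordings are streamed to a storage device, and nothing says rejected windows are erased. Rejection rates by condition and an analysis without rejection would help expose uneven handling; neither is planned.

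**What to change.** Keep the visual review and add the following to the LFP paragraph:

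- Save the rest segments under random codes that hide visit, mode and pre/post, and have the reader mark artifact on the coded files.
- Lock the rejections before the codes are broken.
- Report the percentage of windows rejected by mode and by time.
- Repeat the primary and secondary analyses with no rejection.
- Optionally, add a further sensitivity analysis using a fixed amplitude threshold, set without sight of the labels and applied identically to every segment.

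The cost is a short recoding step, a few sentences of plan text and slightly more analysis. Recruitment, visits and recordings do not change, and no extra staff are needed. If the raw recordings are kept, it can be applied to data already collected. The drawback is that a masked reader loses contextual notes that might help to identify an artifact.
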